6.7.1 Unscheduled Follow-up Visits

If subjects are seen for unscheduled visits because of an AE or additional hand surgery, appropriate Case Report Form(s), will be completed, if applicable.

6.7.2 Loss to Follow-up

If a subject fails to comply with follow-up evaluations, the investigational site must make at least two repeated attempts to contact the subject. Each attempt to contact the subject and the method used (e.g., telephone contact, registered letter) must be documented in the subject's records.

6.8 SUBJECT WITHDRAWAL FROM STUDY

6.8.1 Voluntary Withdrawal

A subject may voluntarily withdraw from the study at any time. If a subject officially withdraws from the study, the investigator must ensure that the reason for the withdrawal is documented. If the subject had an AE, the subject should be followed until the resolution of the AE, if possible. Data from these subjects will be included in the analysis up to the point of each subject's withdrawal.

6.8.2 Involuntary Withdrawal

A subject also may be withdrawn by the investigator if the investigator determines that continued subject participation in the study will have a negative effect on the safety of the subject. Data obtained up to the date of subject withdrawal will be included in the study.

6.8.2.1 During First 3 months following Surgery

• Subjects who have any subsequent surgery on either hand during the first 3 months following their procedure will be withdrawn from the study.

6.8.2.2 After 3 month eVisit:

- Treated Subjects
 - Surgery in the Contralateral Hand Subjects who have subsequent surgery on the contralateral hand (i.e., non-study hand), including CTR, will not be involuntarily withdrawn from the study. Note that a subsequent CTR in the contralateral hand is still not eligible for enrollment in TUTOR.
 - Surgery in the Study Target Hand
 - Subjects who have subsequent surgery on the TUTOR hand that includes the wrist or carpal tunnel region, metacarpals, or thumb (with the exception of trigger thumb release) will be withdrawn from the study.
 - Subjects who have subsequent finger surgery (including trigger finger release) or trigger thumb release that does not affect the wrist or carpal tunnel region will not be withdrawn from the study.

.

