In recent years, multiple studies have demonstrated the feasibility of using ultrasound to perform CTR through even smaller incisions while maintaining or even improving visualization of the carpal tunnel region, including its at-risk neurovascular structures. During CTR with ultrasound guidance (CTR-US), the carpal tunnel is typically accessed through a single small wrist or palmar incision <5 mm length and the TCL is transected using a small knife or similar cutting instrument while the carpal tunnel structures are continuously monitored using US. To date, a total of 13 clinical studies have been published reporting results on over 1300 hands in over 1000 patients at up to 2 years post-treatment comparing recovery time, effectiveness, and safety in subjects with CTS treated with CTR-US or mOCTR with US guidance ¹⁹⁻³¹. Among these over 1300 hands, there were no major neurovascular complications, and the clinical success rate was >95%. Furthermore, two randomized controlled trials and one prospective non-randomized trial demonstrated superior early outcomes for CTR-US compared to mOCTR ^{21,24,28}. However, these trials were limited by small sample size, short follow-up duration, or both. No randomized controlled trial comparing CTR-US to mOCTR has been performed with a sample size over 100 patients and with at least 1 year of follow-up. Thus, the objective of this randomized controlled trial is to compare the safety and effectiveness of CTR-US vs. mOCTR in a large cohort of patients (n=120) with symptomatic CTS followed for 1-year post-treatment.

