10.1 SAMPLE SIZE JUSTIFICATION

The results of the power analysis provided a sample size consisting of 102 evaluable subjects. Group sample sizes of 68 and 34 achieve 80% power to reject the null hypothesis of zero effect size when the population effect size is 0.60 and alpha is 0.05 using a two-sided two-sample equal-variance t-test with a 2:1 randomization allocation. To account for reasonable subject attrition, 120 subjects (n≈80 CTR-US, n≈40 mOCTR) will be enrolled in the trial.

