10.5 DATA ANALYSIS METHODS

Baseline data will be analyzed using descriptive statistics. Continuous data will be summarized using mean and standard deviation for normally distributed data, median and interquartile range for non-normally distributed data, and counts and percentages for categorical data. For categorical variables, percentages will be calculated based on non-missing data.

The percentage of patients in each treatment group that return to normal daily activities within 3 days postoperatively, and the percentage of employed patients in each treatment group that return to work within 3 days postoperatively will be reported and compared using the Fisher's exact test. These outcomes will also be reported as the median and interquartile range in each treatment group. Due to the likelihood that the data distribution may be positively skewed, the nonparametric Mann-Whitney U test will be the statistical test used to assess these endpoints.

Differences between the CTR-US and mOCTR groups with respect to longitudinally measured continuous outcomes (i.e. BCTQ-SSS, BCTQ-FSS, Numeric Pain Scale, EQ-5D-5L) will be analyzed using mixed model analysis and adjusting for the baseline score.

Adverse events will be reported using counts, percentages and exact 95% confidence intervals using Clopper-Pearson's method. The incidence of AEs in each group will be calculated on a per-subject basis and analyzed using Fisher's exact test.

Statistical analyses will be performed using a two-sided hypothesis test at a 5% level of significance. No adjustments for multiplicity are planned. Missing data imputation will not be performed.

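### Repeat surgery on the study hand ends a subject's observation, so scores and new adverse events after a failed release are lost and re-operation itself is not an outcome

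*Combined protocol and SAP*

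**What the plan says.** The objective in section 3 reads: "compare the safety and effectiveness of CTR-US vs. mOCTR in a large cohort of patients (n=120) with symptomatic CTS followed for 1-year post-treatment". Section 7.2 accordingly lists scores and device- or procedure-related adverse events out to 12 months.

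Two rules under Involuntary Withdrawal cut that follow-up short:

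- Section 6.8.2.1: subjects with any later surgery on either "hand during the first 3 months following their procedure will be withdrawn from the study".
- Section 6.8.2.2, after the 3-month visit: subjects whose later surgery involves "the TUTOR hand that includes the wrist or carpal tunnel region, metacarpals, or thumb (with the exception of trigger thumb release) will be withdrawn".

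On what happens to the data, section 6.8.2 says: "Data obtained up to the date of subject withdrawal will be included in the study". Section 10.5 adds: "Missing data imputation will not be performed". Section 6.8.1 asks that a subject with an adverse event be followed to its resolution where possible, but it covers voluntary withdrawal only. Re-operation does not appear among the outcomes in sections 7.1 or 7.2. Section 6.9 contains an exception, not explained further, for a subject who chose another treatment.

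**The concern.** A revision for incomplete release, persistent symptoms or a complication is among the clearest signs that a carpal tunnel release has failed. Under these rules it is also the event that ends data collection. The missing data are then related to outcome, and the amount may differ by arm. The trial is unblinded (section 6.4), so the decision to re-operate could itself depend on the treatment received.

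Two things are at stake. Scores after the revision are absent, so later means lean towards subjects whose first operation held. New adverse events at or after the revision may also go uncollected, and the revision itself has no assured place in the results. The registry in section 5 reported an incomplete release confirmed at re-operation as a complication; this trial names no equivalent outcome.

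The 3-month results are exposed too. Five of the seven main outcomes are at 3 months, inside the period when surgery on either hand leads to withdrawal.

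**Working it through.** **1. The plan's own figure.** Section 10.1 states: "Group sample sizes of 68 and 34 achieve 80% power to reject the null hypothesis of zero effect size". It gives this as the power "when the population effect size is 0.60"; the test is described as "alpha is 0.05 using a two-sided two-sample equal-variance t-test". The noncentrality is 0.60 / √(1/68 + 1/34) = 0.60 / 0.210 = 2.86 on 100 degrees of freedom, which gives exact power of 0.808. The implied attrition is 1 − 102/120 = 15%, and 102/0.85 = 120. The sample size reproduces, and nothing below changes it.

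**2. Following a revision through the plan.**

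- *Trigger.* Revision of the study carpal tunnel leads to withdrawal whenever it occurs, under 6.8.2.1 in the first 3 months and under 6.8.2.2 afterwards.
- *Recording.* Section 6.7.1 calls for a case report form where applicable, if the subject is seen at an unscheduled visit for additional hand surgery. Section 6.9 requires an End of Study form. Adverse events are recorded with the action taken (8.5) and adjudicated (8.6).
- *Counting.* The revision enters a listed outcome only through an adverse event. Section 8 defines that as an adverse change from baseline. A release that leaves symptoms unchanged need not qualify, so a revision for persistent symptoms may be neither an adverse event nor an endpoint. The prespecified event list is on the eCRF and is not shown.
- *Afterwards.* No later collection is described. Section 8.5 finds postoperative events through subject calls and uploaded wound images, and scheduled uploads would presumably stop at withdrawal.

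**3. How many subjects.** The only rate in the documents is the registry's 1/346 = 0.29% (section 5; CTR-US only, in a cohort with 6-month follow-up). Its exact 95% interval is 0.01% to 1.6%. The 5% row is an assumption.

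| Re-operation rate | Expected of 80 | Expected of 40 |
|---|---|---|
| 0.29% (registry) | 0.23 | 0.12 |
| 1.6% (upper limit) | 1.3 | 0.64 |
| 5% (assumed) | 4 | 2 |

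Applying the registry rate to the 40 mOCTR subjects is also an assumption.

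**4. Effect on mean BCTQ-SSS change.** Suppose a fraction f of one arm is withdrawn, would have shown zero change, and is simply omitted. Take the registry's 6-month improvement of 1.6 points for the rest. The arm's mean change is then overstated by 1.6 − 1.6(1 − f) = 1.6f:

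- f = 0.3%: 0.003 × 1.6 = 0.005 points
- f = 1.6%: 0.016 × 1.6 = 0.026 points
- f = 5%: 0.05 × 1.6 = 0.08 points

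With the registry baseline SD of 0.7, the design effect is 0.60 × 0.7 = 0.42 points. The 5% case is 0.08/0.42, about one fifth of that. If both arms lose 5%, the shift largely cancels in the difference.

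**5. Effect on rare events.** Two-sided Fisher tests at 80 versus 40 (illustrations, not forecasts):

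- 0/80 versus 2/40: C(40,2)/C(120,2) = 780/7140, p = 0.109
- 0/80 versus 3/40: C(40,3)/C(120,3) = 9880/280840, p = 0.035
- 4/80 versus 0/40: p = 0.30

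One uncounted subject in the smaller arm can move the result across 0.05. An excess in the larger arm is harder to see: even four events against none give p = 0.30.

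**The case against.** The strongest reply is that the failure comes before the withdrawal, so much of it is already captured. A withdrawn subject was randomized and treated and stays in the modified intention-to-treat population (10.2). Adverse-event incidence is per subject (10.5), so an event already recorded stays in the numerator. Scores before the surgery enter the baseline-adjusted mixed model without imputation, so step 4, which assumes simple omission, ignores information the model would use. All of this stands.

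It also limits three stronger readings that a reader might infer:

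- *The trial stops observing its failures and cannot answer its 1-year question.* Not supported. What is lost is what follows the surgery, plus failures that never qualified as adverse events. Even the statement that follow-up ends is an inference from 6.8.2, though the natural one.
- *Each withdrawn failure moves an arm's event rate by 1/80 = 1.25 or 1/40 = 2.5 points.* True only if that failure was never recorded as an event.
- *The registry rate gives about a 29% chance of at least one revision among 120, from 1 − (345/346)^120.* This applies a CTR-US rate to both arms. For the 80 CTR-US subjects alone it is 1 − (345/346)^80 = 21%.

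The either-hand rule has a rationale, because surgery on the other hand can disturb return to activities, return to work and EQ-5D-5L. Entry criteria also exclude planned contralateral procedures and contralateral symptoms that interfere or are expected to. But bilateral disease is eligible and unplanned surgery remains possible. The documents do not say how often, so no loss of power can be attributed to this rule. The registry's 83% response at 3 months is a separate attrition question.

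The reply does not remove the gap itself: re-operation is not an outcome, following an adverse event to resolution is not written for involuntary withdrawal, and no collection or analysis is planned after the surgery.

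**Conclusion.** The concern holds in a limited form. Observation ends on an outcome-related event, so scores and new adverse events after re-operation are lost, and a revision for persistent symptoms may be counted nowhere. The bias in mean scores is probably small: about 0.005 BCTQ-SSS points at the registry rate, about 0.03 at its upper 95% limit, and 0.08 if 5% of one arm only were affected. The main exposure is the comparison of rare safety and failure events through 12 months, where a single subject can change the test result.

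These sizes assume zero change in a withdrawn failure and simple omission from the analysis. They also rest on a CTR-US registry rate to 6 months, in a cohort selected for having that follow-up, which may be low. The documents give no mOCTR or 12-month rate. This is a should-fix: the main outcomes fall at 3 days and 3 months or concern return to work, and the 12-month results are additional outcomes.

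**What to change.** - **6.8.2.1 and 6.8.2.2.** Replace withdrawal from the study with continued remote questionnaires and adverse-event collection to 12 months, recording the date, hand and reason for the surgery. This changes observation, not care. Voluntary withdrawal and the investigator's safety-based withdrawal are untouched.
- **7.2.** Add repeat carpal tunnel surgery on the target hand through 3 and 12 months, per arm, on all treated subjects, with exact 95% confidence intervals.
- **10.5.** State how scores after surgery are handled: use all scores regardless of later surgery, with sensitivity analyses that (a) count target-hand re-operation as failure or no improvement and (b) exclude scores after any later hand surgery, including the other hand. Analysis (a) is needed because using all scores credits an arm with the benefit of a second operation.
- **6.9.** Clarify the exception for a subject who chose another treatment.

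The cost is a short amendment. The questionnaires are already remote, so no scheduled visits are added, and the sample size stays at 102 evaluable and 120 enrolled. Some scores will reflect the second operation, which the sensitivity analyses address. The change is best made early, because data not collected after a withdrawal may not be recoverable.

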6.9 END OF STUDY

Subjects may exit the study at the end of the study (i.e., the study is discontinued by the Sponsor) or when the subject has completed the 12-month follow-up visit, whichever comes first, unless the subject opted to find an alternative treatment.

An End of Study CRF will be completed at the time the study is completed, discontinued, or lost to follow-up for each subject.

7. OUTCOMES

7.1 MAIN OUTCOMES

7.1.1 Time to Return to Normal Daily Activities within 3 Days

Time to return to normal daily activities will be collected through the ViedocMe ePRO module which asks whether the subject has returned to normal daily activities outside of work. Reminders will be sent to the subjects either by email or text messaging to minimize the risk of missing data. The time to return to normal daily activities will be defined as the number of days between treatment and the time the subject reports returning to normal daily activities, irrespective of work status.

7.1.2 Time to Return to Work Among Employed Subjects

Among study subjects who report full-time or part-time employment, time to return to work will be ascertained through the ViedocMe ePRO module by asking whether the subject has returned to work in full or limited capacity. Return to work within 3 days postoperatively will represent a secondary endpoint of the study. The time to return to work will be defined as the number of days between treatment and the time the subject reports returning to work in any capacity.

7.1.3 BCTQ-SSS Change at 3 Months

The BCTQ is a CTS specific questionnaire that has been shown to be highly reproducible, internally consistent, valid, and responsive to clinical change in CTS and subject status post-CTR. The BCTQ consists of 11 symptom severity questions (BCTQ-SSS). Scoring for the BCTQ-SSS ranges from 1 to 5, with higher scores indicating more severe symptoms, and is calculated as the mean of each response. The between-group mean difference in BCTQ-SSS change scores at the 3-month follow-up will represent a secondary endpoint of the study.

7.1.4 BCTQ-FSS Change at 3 Months

The BCTQ additionally consists of 8 functional status questions (BCTQ-FSS). Scoring for the BCTQ-FSS ranges from 1 to 5, with higher scores indicating more functional limitation, and is calculated as the mean of each response. The between-group mean difference in BCTQ-FSS change scores at the 3-month follow-up will represent a secondary endpoint of the study.

7.1.5 Numeric Pain Scale Change at 3 Months

Subjects will be asked to rate their wrist pain severity on a scale of 0 to 10, where 0 represents "no pain" and 10 represents "worst possible pain". The between-group mean difference in Numeric Pain Scale change scores at the 3-month follow-up will represent a secondary endpoint of the study.

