3. BACKGROUND AND OBJECTIVE

Carpal tunnel syndrome (CTS) is the most common peripheral neuropathy, affecting approximately 5% of the population ¹. A multitude of treatments are available to treat CTS, including activity modification, bracing/splinting, hand therapy, modalities (e.g., therapeutic lasers or ultrasound, iontophoresis), acupuncture, corticosteroid injections, and carpal tunnel release (CTR) surgery performed using an open or an endoscopic approach ²⁻⁷. Currently, there is no universally accepted algorithm to guide treatment for patients suffering with CTS. The American Academy of Orthopedic Surgery (AAOS) CTS Clinical Practice Guidelines reported that only three treatments are strongly supported in the literature: splinting, corticosteroid injections, and CTR ⁴. Although some patients with mild-moderate symptoms are successfully treated with splinting and/or corticosteroid injections, those with progressive, refractory, or severe symptoms generally proceed to CTR for definitive management ^{2,3,5-9}.

[figure not shown]
The goal of CTR is to reduce median nerve pressure by dividing the transverse carpal ligament (TCL) while avoiding iatrogenic injury to surrounding neurovascular structures. Among the ~600,000 CTR procedures performed in the United States annually ^{1,10}, most (70-80%) use a traditional open technique (OCTR) during which a palmar incision is made to dissect down to the TCL and transect it using a scalpel, scissors, or a similar cutting device ¹¹⁻¹³. The OCTR technique requires a relatively large (3-5 cm) incision and may be associated with a prolonged recovery period due to palmar pain and the need to protect the wound ^{12,14-17}.

Over time, there has been a trend to use smaller incisions (1-3 cm) to reduce surgical morbidity using mini-OCTR (mOCTR) or endoscopic CTR ^{11,16,17,19}. Because long-term outcomes and complication profiles are generally equivalent among these CTR procedures ¹⁸, factors related to patient recovery time such as time to return to normal activities and work absenteeism are important considerations that may assist in shared decision-making between physicians and patients.

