4. DEVICE DESCRIPTION

The UltraGuideCTR (Sonex Health, Inc., Eagan, MN) is a commercially available medical device specifically developed to facilitate CTR-US. The device is a single-use, hand-held device that is inserted into the carpal tunnel through a small (typically < 5 mm) wrist incision using continuous US guidance. The working tip of the UltraGuideCTR consists of two inflatable balloons that border a centrally located, retractable retrograde cutting knife. When inflated with sterile saline, the balloons increase the diameter of the tip from 4 mm to 8 mm. After the tip is positioned within the transverse safe zone, the balloons are inflated to create space in the carpal tunnel, the blade is activated, and the TCL is transected in a retrograde manner. Following TCL transection, the blade is recessed, the balloons deflated, and the device is removed. The TCL is probed to ensure a complete release. The entire procedure is performed using US guidance. The first commercial CTR-US procedure with the device was performed in February 2017. Since then, over 100 different physicians have been trained to use the UltraGuideCTR, who collectively have performed over 15,000 procedures. Labeled images of the device are provided below.

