6.2.1 Inclusion Criteria

- 1. \geq 18 years of age
- 2. Clinical diagnosis of unilateral or bilateral idiopathic CTS
- 3. CTS-6 score >12 in target hand
- 4. Absence of carpal tunnel symptoms in the contralateral hand that interfere with normal daily activities or work at the time of consent and are not anticipated to interfere with return to activities or return to work within at least 3 months post-operatively
- 5. Median nerve cross-sectional area ≥10 mm² in the proximal carpal tunnel region of the target hand measured by diagnostic ultrasound
- 6. Prior failure of one or more nonsurgical treatment options for the target hand (e.g., physical activity modification, bracing, splinting, corticosteroid injection)
- 7. Subject agrees to complete follow-up questionnaires over a 12-month period
- 8. Subject has a valid mobile phone number and email address to receive and answer follow-up questionnaires

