6.3 RANDOMIZATION

Subjects meeting all study inclusion/exclusion criteria after their screening evaluation will be randomized. This study will enroll 120 subjects who will be randomized in 2:1 fashion to receive CTR-US (n≈80) or mOCTR (n≈40). The randomization sequence for this trial will be computer-generated by the electronic data capture system (Viedoc). The randomization

sequence will be stratified by site with variable block sizes. Treatment assignment will be concealed until it is presented to authorized site personnel at the time of randomization. Only randomized and treated subjects will be considered enrolled in the study. Randomized patients who do not receive their assigned treatment will be discontinued from the trial.

6.4 **BLINDING**

Owing to obvious differences in surgical technique, it is not possible to blind the treating physicians. Owing to notable visual differences in the postoperative scar between surgical techniques (3-5 mm for CTR-US and approximately 3 cm for mOCTR), it is not possible to blind the subjects. Owing to the fact that all data collected in this trial will be self-reported, it is not possible to blind outcome assessors (i.e., subjects).

6.5 **PROCEDURE**

The key procedural steps involved in CTR-US are listed below.

- 1. Using direct US visualization, identify relevant anatomical structures within the carpal tunnel.
- 2. Dissect synovial tissue from the undersurface of the TCL via hydrodissection.
- 3. Insert the device through a small wrist incision and advance into the carpal tunnel.
- 4. Position the tip of the device distal to the distal TCL so that the TCL Blade will engage the distal TCL.
- 5. Confirm the position of the device under ultrasound.
- 6. Activate the Stealth MicroGuard balloons to create space within the carpal tunnel.
- 7. Deploy the TCL Blade by moving the slide button proximally to transect the TCL from distal to proximal until the TCL Blade passes into its proximal recessed position.
- 8. With the device or an elevator, probe the TCL to ensure a complete release.

Complete procedural details are provided in the Instructions for Use (https://sonexhealth.com/physicians/ultraguidectr/instructions-for-use).

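### The pain item asks about the wrist only and names no side, so it may under-record incision pain after mini-open release and can pick up pain from the other wrist

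*Combined protocol and SAP*

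**What the plan says.** Section 7.1.5 gives the only definition of the pain item: "Subjects will be asked to rate their wrist pain severity on a scale of 0 to 10". It fixes the two ends of the scale and then the role of the measure: "The between-group mean difference in Numeric Pain Scale change scores at the 3-month follow-up will represent a secondary endpoint of the study". The same measure is listed among the main outcomes in the synopsis. Section 7.2 adds pain change at 2 weeks and at 1, 6 and 12 months, and the patient-reported table in Section 6.7 also collects it at baseline, on the procedure day, post-op and daily on days 1 to 14. Nowhere is the item extended to the palm, the scar or the hand, or tied to a side.

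On where the wounds lie:

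- Section 3 says that most releases "use a traditional open technique (OCTR) during which a palmar incision is made", and that this technique "may be associated with a prolonged recovery period due to palmar pain and the need to protect the wound".
- Section 3 then introduces the comparator: "there has been a trend to use smaller incisions (1-3 cm) to reduce surgical morbidity using mini-OCTR (mOCTR) or endoscopic CTR".
- Section 4 says the study device goes in "through a small (typically < 5 mm) wrist incision using continuous US guidance"; step 3 of Section 6.5 agrees.
- Section 6.4 gives the scar lengths as "3-5 mm for CTR-US and approximately 3 cm for mOCTR". It gives no site for the mini-open incision.

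On sides, Section 6.2.1 admits "Clinical diagnosis of unilateral or bilateral idiopathic CTS". The criteria on CTS-6 score, nerve area and failed nonsurgical treatment all specify the target hand. The pain item does not.

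**The concern.** A pain scale compares two operations fairly only if it covers the area where each may hurt. This item names the area where the study device enters. If the mini-open incision lies in the palm, as the account of open release suggests, some subjects in that arm may have a sore palm and a comfortable wrist and give a low score, while a CTR-US subject with a sore entry site scores it in full. The subjects are unblinded and rate themselves, so no assessor can correct for how they read the question.

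At stake are the 3-month pain comparison and, more so, the early pain results, when incision pain is likely to matter most. The missing side is a separate gap: a subject with symptoms or surgery in the other hand is not told which wrist to rate.

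**Working it through.** **1. Wound site against item area**

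| | CTR-US | mOCTR |
|---|---|---|
| Incision site | wrist (Sections 4, 6.5) | not stated; traditional open release is palmar (Section 3) |
| Scar length (Section 6.4) | 3-5 mm | about 3 cm |
| Covered by an item naming the wrist | yes | uncertain |

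The mini-open scar is 30/5 = 6 to 30/3 = 10 times as long, and it is the one that may lie outside the named area. Section 3 allows a palmar entry for ultrasound-guided release in general, but the device used here enters at the wrist.

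**2. Effect on the comparison**

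Let M and C be true mean pain in the study hand after surgery (mOCTR, CTR-US), and let u_m and u_c be the mean points that the item leaves unrecorded in each arm.

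Recorded difference = (M − u_m) − (C − u_c) = (M − C) − (u_m − u_c).

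The error is u_m − u_c. If u_m exceeds u_c, pain after mOCTR is understated relative to CTR-US, and any advantage of CTR-US shrinks. Before surgery there is no incision, so unrecorded incision pain enters the change score in full and looks like extra improvement. The baseline adjustment in Section 10.5 cannot remove it, because it arises after baseline. Both terms should fall as the wounds heal, so the gap is probably largest in the early weeks and smaller at 3 months.

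The sign is probable, not certain. In CTR-US the ligament is cut from its distal end (Section 6.5), so pain away from the entry site is possible there too, and u_c need not be zero.

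**3. What the documents allow on size**

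They give no value for u_m or u_c, no standard deviation for pain, and no expected pain difference. The only effect size is 0.60 in Section 10.1, which is attached to no outcome. That figure reproduces. For a two-sided equal-variance t-test with 68 and 34 subjects, df = 100 and the noncentrality is d × √(68 × 34/102) = 4.761d. At d = 0.60 this is 2.857 and power is 80.8%, against 80% stated (79.6% at 66 and 33).

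As an illustration only, assume that the true standardized pain difference is 0.60 and that the item keeps part of it:

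| Share kept (assumed) | d | Noncentrality | Power at 68/34 |
|---|---|---|---|
| 100% | 0.60 | 2.857 | 81% |
| 90% | 0.54 | 2.571 | 72% |
| 75% | 0.45 | 2.142 | 56% |
| 50% | 0.30 | 1.428 | 29% |

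This shows how sensitive a comparison of this size is to lost signal. It does not estimate the loss.

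**4. The missing side, by period**

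- *To 3 months.* Inclusion criterion 4 rules out contralateral symptoms that interfere with activities or work, or are expected to. Exclusions 3 and 11 bar recent contralateral release and planned contralateral procedures. Section 6.8.2.1 withdraws anyone operated on either hand. What remains is contralateral symptoms that do not interfere.
- *After 3 months.* Section 6.8.2.2 keeps subjects who have contralateral surgery, carpal tunnel release included. At 6 and 12 months a subject may have a recently operated other wrist and a question that does not say which one is meant.

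Nothing suggests that this differs by arm, so its main effect is noise.

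**The case against.** The strongest reply is that the link to this comparator is inferred. The sentence on palmar pain concerns traditional open release with a 3-5 cm incision. The comparator is the mini-open form, which Section 3 presents as a way to lessen surgical morbidity, and its incision site is not given. This stands, and it is why the point says that the item may under-record pain. Carry-over is still reasonable, because the protocol describes mini-open release as a smaller version of the same operation.

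A reader might infer that the item misses the comparator's pain altogether. The documents do not support that. Some subjects will count palm pain as wrist pain, pain at the wrist after mOCTR is still scored, and disease-related wrist pain is scored in both arms. The on-screen wording is not in the documents and may be fuller than Section 7.1.5.

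A reader might also multiply an assumed share of subjects by an assumed number of points and call the product the bias. Neither input has a source, and such a figure sets unrecorded pain in CTR-US to zero. Nor does the protocol state a hypothesis about palmar pain that this item fails to test: its rationale is recovery time, and its objective is safety and effectiveness.

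Other measures bear on pain. EQ-5D-5L has a pain/discomfort domain with no body site, and pain medication is recorded throughout. They soften the gap but do not close it: the domain is one of five, is not tied to the operated hand, and is planned only within the overall EQ-5D-5L change.

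Finally, the likely direction is against the sponsor's device, so the item is unlikely to create a false benefit. That is fair, but a measure that may hide a real difference is still worth correcting.

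**Conclusion.** The point holds as a defect in how a stated measure is worded. The item covers the wrist and no side; the device enters at the wrist; and the only account of open release places its incision and its pain in the palm. Incision pain may therefore be recorded unequally by arm, most likely in the early weeks and probably to the disadvantage of CTR-US. This rests on two assumptions: that the mini-open incision lies at least partly in the palm, and that some subjects separate palm from wrist when they answer. The size cannot be computed from the documents, and the effect on the 3-month comparison is probably smaller than on the early ones.

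The side gap is real but smaller. The eligibility and withdrawal rules limit it up to 3 months, and after that it mainly adds noise. A reader might take it as a source of bias between arms; nothing in the documents supports that.

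The correction should be made because it is specific and nearly free. The finding does not make the pain results unusable.

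**What to change.** In Section 7.1.5 and in the ePRO module, define the item as pain in the target hand, with left or right shown, including the wrist, palm and incision area, on the same 0-10 scale. Use identical wording in both arms and at every time point, baseline included. Take the side from screening, where the target hand is already identified; Section 6.3 does not say that the randomization record holds it. If the screen text already names these areas and the side, bring Section 7.1.5 into line with it. State the mini-open incision site in the protocol as well, so that a reader can judge what the item covers.

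The cost is a wording change in the protocol and the ePRO module, with no added burden on subjects. If enrollment has begun, keep each subject on the version used at that subject's baseline, so that change scores never mix versions. Record the version, and include it as a covariate in the mixed model or examine it in a sensitivity analysis. A covariate adjusts for a difference in level between versions but does not recover pain that the wrist-only item left out, so the estimate from subjects on the new version should be shown alongside the overall one.
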